## Figure 1. Overall Study Design

The dose of each component evaluated in subsequent cohorts was determined based on the safety data from previous cohorts.

The treatment effect of cancer immunotherapy can often be delayed. Therefore, participants should be encouraged to continue on study treatment for at least 24 weeks before an investigator considers removing the participant due to disease progression, as long as:

- Participant and investigator agree.
- Participant continues to meet all other study protocol eligibility criteria.
- Acceptable toxicity.
- No deterioration of participant performance status.

If a participant withdraws from the study before Day 29 for reasons other than investigational product-related toxicity, another participant may be enrolled to replace that participant at the current dose level. In principle, all participants must be evaluated for 28 days following the first AdC68 vaccination. However, if a participant discontinues close to Day 29 for reasons other than toxicity, but due to a clear drug unrelated event (eg, traffic accident, clear disease progression), the participant may be deemed evaluable for safety if the investigator and sponsor's medical monitor both agree that the participant is suitable for inclusion in the dose limiting toxicity (DLT) evaluation group.

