4.3. Sample Size Determination

The exact sample size of the 3+3 designs in the Phase 1 Part A (Dose Escalation) cannot be pre-specified because of the dynamic feature of the design. The number of patients to be enrolled in the study will depend upon the observed safety profile, which will determine the number of patients at each dose level (eg, 3 or 6) and the number of dose levels explored.

Typically, at least 3 patients will be treated at each regimen dose level. Dose cohorts with an acceptable safety profile (0/3 or 1/6 patients with DLTs) may be expanded up to N=15 to further assess safety, immune response, pharmacokinetics, and pharmacodynamics.

Decisions to enroll additional patients at dose levels already cleared for safety will be based on clinical judgment of the investigators and the sponsor considering all evaluable safety, immunoresponse, and/or pharmacodynamics data.

The estimated sample size for Part A would be 24-48 patients and will be dependent on the safety profile observed.

The sample size for Cohort 1B (AdC68 + pDNA + tremelimumab 80 mg SC for BCR patients who had no prior therapy) was determined clinically rather than statistically. Twenty patients were enrolled in that cohort to provide preliminary efficacy, safety, PK and biomarker data for this regimen.

For Cohort 3B (AdC + pDNC + tremelimumab 80 mg SC + PF-0689159 300 mg SC for patients with mCRPC whose disease has progressed despite novel hormonal treatment), 18 patients

were enrolled. The main efficacy endpoint for this cohort will be objective response rate (ORR) based on RECIST version 1.1, the key supportive efficacy endpoint will be radiographic progression-free survival (rPFS). There are no hypothesis tests for these endpoints. Bayesian approach may be used to evaluate the efficacy data. For example, Bayesian approach with a non-informative Jeffery's prior beta (0.5,0.5) will be used to calculate the posterior probability the ORR of the study treatment exceeds various ORR thresholds of interest in the end of the study.

For Cohort 5B (AdC68 + pDNA + tremelimumab 80 mg SC + PF-0689159 130 mg SC. for BCR patients who had no prior therapy), the sample size was determined clinically rather than statistically. Fifteen patients were enrolled in that cohort to provide preliminary efficacy, safety, PK and biomarker data for the regimen.

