8.1.3. Exploratory (Part A) / Secondary (Part B) Efficacy Analyses

In this First-In-Patient study anti-tumor activity is an exploratory objective. The main analysis populations will be based on mITT and EP.

Tumor response, using RECIST, irRECIST, will be presented in the form of patient data listings which include, but are not limited to tumor response assessed in comparison to baseline. Traditional response measures in solid tumors, such as ORR and PFS were developed to evaluate chemotherapies and can be unreliable for tracking response to immunotherapies such as cancer vaccines. For example, apparent tumor burden may increase during the first few months of cancer vaccine treatment because of inflammation/T cell infiltration into tumors even in patients who go on to have durable responses. Time to progression and number of patients with progression could be calculated from first vaccination (Cycle 1 Day 1), but may also be calculated excluding those progressions that happened before some specific timepoints (eg, Day 57, Day 113). Time to response will be calculated from first vaccination (Cycle 1 Day 1) to time of first response (ie, CR or PR).

Additionally, total measurable tumor burden will be evaluated by the irRECIST criteria that include responses after disease progression that are not captured by RECIST evaluation criteria in solid tumors.

For tumor response data, the following analyses may be performed:

1. Tumor response (CR, PR, SD, PD, etc.) by cohort and visit, separately for RECIST 1.1 and irRECIST. Investigator provided tumor response will be presented by descriptive statistics (frequency and percentage).
2. Best overall response, by cohort, **across all available tumor assessments from both treatment period and maintenance period**, separately for RECIST 1.1 and irRECIST. Best overall response will be derived programmatically. In the tabular data presentation, a row of CR+PR will be added to show the results of ORR. With RECIST 1.1, tumor response (CR or PR) confirmation is optional as response rate is not the primary endpoint of the study, hence unconfirmed best overall response will be derived and presented. With irRECIST, tumor response (irCR or irPR) and disease progression (irPD) are required to be confirmed, however in this study tumor response confirmation is not required, therefore unconfirmed best overall response will be derived and presented. Descriptive statistics (frequency and percentage) will be provided.

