10.4. Appendix: Immune-related Response Criteria per RECIST 1.1 (irRECIST)

Immune-related progressive disease (irPD) needs to be confirmed by a second, consecutive assessment at least 4 weeks apart. irPD is also considered to be confirmed if the patient:

- dies within 12 weeks after the initial observation of irPD, or
- discontinues treatment due to disease progression (clinical deterioration without radiological documentation) prior to or within 12 weeks after the assessment of irPD.

Immune-related Best Overall Response (irBOR) will be derived based on reported lesion responses at different evaluation time points from the start date until confirmed immune-related disease progression per irRECIST, according to the following rules.

[figure not shown]
- Confirmed irCR = at least two determinations of irCR at least 4 weeks apart before irPD.
- Unconfirmed irCR = one determination of irCR before irPD (and not qualifying for confirmed irCR or irPR).
- Confirmed irPR = at least two determinations of irPR or better at least 4 weeks apart before irPD (and not qualifying for confirmed irCR).
- Unconfirmed irPR = one determination of irPR before irPD (and not qualifying for confirmed irCR or irPR or unconfirmed irCR).
- irSD = at least one irSD or irPD assessment ≥ 6 weeks after start date and before confirmed irPD (and not qualifying for confirmed/unconfirmed irCR or irPR).
- irPD = ≤ 12 weeks after the first dose of study treatment and at least two consecutive determinations of irPD at least 4 weeks apart. irPD is also considered to be confirmed if the patient:
 - dies within 12 weeks after the initial observation of irPD, or
 - discontinues treatment due to disease progression (clinical deterioration without radiological documentation) prior to or within 12 weeks after the assessment of irPD.
- NE: All other cases.

Only tumor assessments performed before the start of any further anti-cancer treatment will be considered in the assessment of irBOR.

Immune-related Objective Response (irOR) is defined as irCR or irPR according to irRECIST from start date until confirmed irPD or death due to any cause. Both irCR and irPR must be confirmed by repeat assessments performed no less than 4 weeks after the criteria for immune-related response are first met. Also, irPD must be confirmed by a

second, consecutive assessment at least 4 weeks apart. Immune-related OR rate (irORR) is the proportion of patients with irOR in the analysis set.

CCI

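### RECIST 1.1 best overall response has no visible stop at first progression, so read literally a progression that later reverses would count towards Cohort 3B's ORR

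*SAP*

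**What the plan says.** SAP 4.3 sets the role of the endpoint: "The main efficacy endpoint for this cohort will be objective response rate (ORR) based on RECIST version 1.1". Protocol 9.3 says the same and adds a Beta(0.5, 0.5) prior with a worked example of 6 responders in 18.

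SAP 8.1.3 item 2 gives the derivation, for RECIST 1.1 and irRECIST separately but with one shared window:

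- "Best overall response will be derived programmatically";
- the assessments used are those "across all available tumor assessments from both treatment period and maintenance period";
- "a row of CR+PR will be added to show the results of ORR";
- for RECIST 1.1, confirmation is optional, "hence unconfirmed best overall response will be derived and presented".

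The paragraph on irRECIST in the same section explains why it is used alongside RECIST: its criteria "include responses after disease progression that are not captured by RECIST evaluation criteria in solid tumors".

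For irRECIST, SAP Appendix 10.4 narrows the window. Immune-related best overall response (irBOR) runs from the start date to confirmed irPD, and "Only tumor assessments performed before the start of any further anti-cancer treatment will be considered in the assessment of irBOR". The PSA-50 definition in SAP 8.1.3 also stops at other systemic anti-cancer therapy. No visible text does either for RECIST 1.1. Protocol Appendix 3 defines status at each evaluation and has no best-overall-response rule. SAP 10.3 defers rules to a programming specification only for PFS and rPFS. The closing bullets of SAP 10.4 refer to sections on the RECIST endpoints, but the section number is an unfilled placeholder.

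**The concern.** Best overall response is the best status over a window, so the end of the window decides the result for anyone who progresses and later shrinks. This design can produce such participants. The text under Figure 1 in Protocol 3.1 says "participants should be encouraged to continue on study treatment for at least 24 weeks" before removal for progression is considered, subject to four conditions. Scans are every 8 weeks from Cycle 1 Day 1. Protocol 6.4.1 bases withdrawal for objective progression on irRECIST with confirmation, not on a first RECIST PD. SAP 8.1.3 itself expects apparent early growth in some participants who later respond.

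If the program follows item 2 literally, the RECIST rate takes in some of the delayed responses that irRECIST is there to show, and the contrast between the two rates is blurred. Such a participant would be an rPFS event at first PD and a RECIST responder at a later visit. His response would begin after his progression, so his RECIST duration of response would have no clear meaning.

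**Working it through.** **1. Inputs.** Cohort 3B n = 18 (Protocol 9.3, SAP 4.3). Prior Beta(0.5, 0.5) (same sections). Threshold 25% (the example in Protocol 9.3). No confirmation needed (SAP 8.1.3). Scans at weeks 8, 16 and 24 (schedule of activities). The number of participants whose RECIST PD later reverses is not in the documents; 0 to 3 is assumed below.

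**2. The plan's own figure.** With r responders the posterior is Beta(r + 0.5, 18 − r + 0.5). For r = 6 this is Beta(6.5, 12.5), and P(ORR > 0.25) = 0.797. The protocol says about 80%, so its figure is reproduced.

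**3. One participant under two windows.** Take target sums of 100 at baseline, then 125, 110 and 65 at weeks 8, 16 and 24, with no new lesions and no non-target progression. Target PD is taken as a rise of at least 20% from nadir. That is an assumption: the visible RECIST text in Appendix 3 only implies it, through its definition of stable disease.

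| Week | Sum | Change | Status at visit |
|---|---|---|---|
| 8 | 125 | +25% from nadir 100 | PD |
| 16 | 110 | +10% from nadir 100 | SD |
| 24 | 65 | −35% from baseline | PR |

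Best status over all available assessments is PR, a responder. Best status up to and including the first PD is PD, a non-responder.

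**4. Direction.** The best status over a longer window cannot be worse than over a shorter one. Every responder under the stopped window is also a responder under the literal one, so the literal window can only raise ORR.

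**5. Size.** Each affected participant changes ORR by 1/18 = 5.6 percentage points. Starting from the protocol's example of 6/18 and removing those whose only response came after PD:

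| Removed | r/18 | ORR | P(ORR > 25%) |
|---|---|---|---|
| 0 | 6/18 | 33.3% | 0.797 |
| 1 | 5/18 | 27.8% | 0.623 |
| 2 | 4/18 | 22.2% | 0.410 |
| 3 | 3/18 | 16.7% | 0.212 |

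One such participant moves the posterior probability by 0.797 − 0.623 = 0.174; two move it by 0.797 − 0.410 = 0.387.

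**6. Which progressions can reverse.** Under Table 1 of Protocol Appendix 3, a visit with a new lesion or with non-target PD is PD whatever the target lesions do. A later PR is therefore possible only where PD came from target growth that reverses, or where the new lesion or non-target progression is no longer present at the later visit.

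**The case against.** The strongest reply is that the SAP never says a response after progression counts under RECIST. The phrase in item 2 can be read as saying only which study periods are pooled, and the one sentence on the subject says RECIST does not capture such responses. That is fair. A reader might infer that the plan has adopted a rule counting post-progression shrinkage; the documents do not support that. What stands is that the operative instruction gives a window with no stop, while the contrary statement is background. If the background sentence is the intent, the instruction should say so.

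A reader might also infer that any shrinkage after PD would count, or that responses to a later therapy would enter ORR. Neither goes far. A persisting new lesion keeps later visits at PD. The window is the treatment and maintenance periods, Protocol 5.7.2 bars other anti-tumour treatment during study treatment, and scheduled imaging ends at permanent discontinuation or at progression needing a new modality. Continued treatment is conditional, and Protocol 3.1 also lists progression as a reason to stop, so post-PD scans may exist but are not certain.

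The stakes are limited too. ORR is a Part B secondary endpoint without a hypothesis test. SAP 4.3 says a Bayesian approach may be used, and Protocol 9.4 says the Bayesian results may be left out of the study report. The 25% threshold is only an example. Protocol 4.1.2 asks for measurable disease in at least about 40% of Part B participants, which is 0.40 × 18 = 7.2, so near that floor 6 responders would be an extreme result. Displays by visit could reveal a PD followed by PR. Redacted text or the programming specification may already hold a stop. These points lower the severity, but they do not supply the missing rule for the cohort's main efficacy endpoint.

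**Conclusion.** The point holds as an inconsistency that needs a clarifying rule, at should-fix level. Taken literally, item 2 would make a RECIST responder of a participant whose PD reverses during continued treatment. That conflicts with the section's own account of RECIST and with the irBOR window in SAP 10.4. The bias, if any, is upward: nothing if no such participant exists, and 5.6 points of ORR for each one. In the protocol's example, one such participant is the difference between 0.62 and 0.80 for P(ORR > 25%). The conclusion rests on the visible text, on an assumed number of affected participants, and on a 20% rise from nadir as target PD.

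Because SAP 8.1.3 counts PCWG3 bone progression as an rPFS event, a reader might infer that it should also close the response window. The documents do not support that. They define ORR by RECIST 1.1 and bone outcome by PCWG3 as separate endpoints and combine the two only for rPFS. A bone stop would change the endpoint and could remove genuine RECIST responders.

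**What to change.** In SAP 8.1.3 item 2, add for RECIST 1.1: *Best overall response per RECIST 1.1 is derived from assessments from the first vaccination up to and including the first RECIST 1.1 PD, and before the start of any new anti-cancer therapy.* The second condition has small practical reach but brings the rule into line with irBOR and PSA-50.

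Apply the same window to RECIST time to response, RECIST duration of response and the ORR used in the posterior probability. Leave later responses to irRECIST, within its Appendix 10.4 window, and to the by-visit tables, listings and plots. Do not add PCWG3 bone progression as a stop for RECIST ORR. Fill in the placeholder reference to the RECIST sections at the end of SAP 10.4. If the programming specification already has a stop, copy it into the SAP.

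The cost is one sentence and one programming condition. The downside is that the RECIST ORR may be slightly lower.

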### **9.3. Sample Size Determination**

The exact sample size of the 3+3 designs in the Phase 1 Part A (Dose Escalation) cannot be pre-specified because of the dynamic feature of the design. The number of patients to be enrolled in the study will depend upon the observed safety profile, which will determine the number of patients at each dose level (eg, 3 or 6) and the number of dose levels explored.

Typically, at least 3 patients will be treated at each regimen dose level. Dose cohorts with an acceptable safety profile (0/3 or 1/6 patients with DLTs) may be expanded up to N=15 to further assess safety, immune response, pharmacokinetics, and pharmacodynamics. Decisions to enroll additional patients at dose levels already cleared for safety will be based on clinical judgment of the investigators and the sponsor considering all evaluable safety, immunoresponse, and/or pharmacodynamics data.

The estimated sample size for Part A would be 24-48 patients and will be dependent on the safety profile observed.

The sample size for Cohort 1B (AdC68 + pDNA + treme 80 mg SC for BCR patients who had no prior therapy) was determined clinically rather than statistically. Twenty patients were enrolled in that cohort to provide preliminary efficacy, safety, PK and biomarker data for this regimen.

For Cohort 3B (AdC + pDNC + treme 80 mg SC + PF-0689159 300 mg SC. for patients with mCRPC whose disease has progressed despite novel hormonal treatment), 18 patients were enrolled. The sample size was determined clinically rather than statistically. The smaller sample size was determined to be adequate for continued safety analysis. The main efficacy endpoint for this cohort will be objective response rate (ORR) based on RECIST version 1.1. There are no hypothesis tests for these endpoints. Bayesian approach with a non-informative

Jeffery's prior beta (0.5,0.5) will be used to calculate the posterior probability the ORR of the study treatment exceeds various ORR thresholds of interest in the end of the study. For example, if 6 responders were observed in the 18 patients, the posterior probability that the true ORR is greater than 25% would be about 80%.

For Cohort 5B (AdC68 + pDNA + treme 80 mg SC + PF-0689159 130 mg SC. for BCR patients who had no prior therapy), the sample size was determined clinically rather than statistically. Fifteen patients were enrolled in that cohort to provide preliminary efficacy, safety, PK and biomarker data for the regimen.

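### SAP 8.1.3 derives only an unconfirmed RECIST ORR, although ORR is Cohort 3B's main efficacy endpoint; a confirmed ORR should be shown beside it

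*SAP*

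**What the plan says.** **Role of ORR.** For Cohort 3B, SAP 4.3 states: "The main efficacy endpoint for this cohort will be objective response rate (ORR) based on RECIST version 1.1". Protocol 9.3 says the same and gives the cohort size: "18 patients were enrolled. The sample size was determined clinically rather than statistically". Protocol 3.1.2 describes the cohorts as non-randomized, so the cohort has no concurrent control.

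**Use of ORR.** SAP 4.3 first says "Bayesian approach may be used to evaluate the efficacy data". It then gives as an example a Jeffreys "prior beta (0.5,0.5) will be used to calculate the posterior probability the ORR of the study treatment exceeds various ORR thresholds of interest". Protocol 9.3 illustrates this: "if 6 responders were observed in the 18 patients, the posterior probability that the true ORR is greater than 25% would be about 80" (per cent).

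**Derivation of ORR.** SAP 8.1.3 item 2 takes best overall response over every available assessment in the treatment and maintenance periods. It waives RECIST confirmation and gives its reason: "With RECIST 1.1, tumor response (CR or PR) confirmation is optional as response rate is not the primary endpoint of the study". Only the version without a repeat scan is therefore produced, and in the table of best overall response "a row of CR+PR will be added to show the results of ORR". Neither document describes any other RECIST ORR. Protocol Appendix 3 has no confirmation rule for RECIST responses.

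**Other response measures.** The PSA-50 definition in SAP 8.1.3 needs two consecutive qualifying values at least 3 weeks apart. SAP Appendix 10.4 requires irCR and irPR to be confirmed at least 4 weeks later, although SAP 8.1.3 item 2 waives this for irRECIST best overall response.

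**The concern.** The reason given for waiving confirmation looks at the study's primary endpoint. It does not consider what SAP 4.3 asks of ORR within Cohort 3B, where it is the leading efficacy measure and is set against fixed thresholds.

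On the same data, confirmed responders are a subset of unconfirmed responders, so the unconfirmed count can never be the smaller. One favourable reading is enough to gain a response, and a later scan cannot remove it. With no control arm, nothing offsets over-called responses. With 18 patients, one response more or less moves the posterior noticeably.

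At stake is how the sponsor reads preliminary efficacy. Protocol 3.1.2 says the sample is large enough for decisions about further development that rest on safety and preliminary efficacy. No test or error rate is affected, since SAP 4.1 plans no hypothesis test.

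**Working it through.** **Inputs**
- n = 18 (Protocol 9.3, SAP 4.3).
- Prior Beta(0.5, 0.5) (Protocol 9.3, SAP 4.3).
- Example: 6 responders, 25% threshold, about 80% (Protocol 9.3).
- Two mCRPC cohorts together, n = 33 (Protocol Document History, Amendment 8 rationale). Protocol 9.4 and SAP 8.1.3 allow Cohorts 7A and 3B to be combined.
- Rate at which responses fail confirmation: not given. I assume 0 to 3 of the example's 6 responders.

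**Formula.** With k responders in n patients, the posterior is Beta(k + 0.5, n − k + 0.5). The quantity wanted is its upper tail above the threshold t.

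**Step 1: the plan's own figure.** k = 6, n = 18 gives Beta(6.5, 12.5), and P(ORR > 0.25) = 0.797. This agrees with the Protocol's figure. A flat Beta(1, 1) prior would give 0.825, so the stated value is the Jeffreys one. The example is correct; the question is which responders count.

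**Step 2: responses failing confirmation, n = 18**

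| Failing (assumed) | k | P(ORR > 25%) | P(ORR > 20%) | P(ORR > 15%) |
|---|---|---|---|---|
| 0 | 6 | 0.797 | 0.915 | 0.977 |
| 1 | 5 | 0.623 | 0.801 | 0.927 |
| 2 | 4 | 0.410 | 0.615 | 0.811 |
| 3 | 3 | 0.212 | 0.383 | 0.608 |

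At 25%, the first loss costs 0.797 − 0.623 = 0.174 and the second 0.623 − 0.410 = 0.213. At 20%, they cost 0.915 − 0.801 = 0.114 and 0.801 − 0.615 = 0.186.

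**Step 3: pooled mCRPC cohorts, n = 33.** To keep the example's observed rate of one third, take k = 11. P(ORR > 25%) is 0.865 for 11/33, 0.764 for 10/33 and 0.630 for 9/33. The first loss costs 0.865 − 0.764 = 0.101 and the second 0.764 − 0.630 = 0.134.

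**Step 4: is a confirming scan available?** The Schedule of Activities tumor-assessment note asks for CT or MRI every 8 weeks (± 5 days). A second reading at least 4 weeks after the first therefore falls within the existing schedule for any participant still being scanned. Scanning stops at permanent discontinuation, death, or progression that needs a new treatment, so a response first seen at the last scan could not be confirmed.

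**The case against.** **The documents do not contradict themselves.** A reader might infer that SAP 8.1.3 conflicts with SAP 4.3. It does not. ORR can lead the efficacy measures of one cohort without being the study's primary endpoint, and SAP 6.4 and Protocol 2.3 both make safety primary in Part B. Unconfirmed ORR is a disclosed, pre-specified choice that breaks no rule in Protocol Appendix 3. This objection stands in full.

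**The link to a decision is loose.** A reader might infer that this posterior settles the development decision. The documents do not say so. The Bayesian analysis is optional in SAP 4.3, and under Protocol 9.4 it may be left out of the clinical study report. No single threshold or cut-off is fixed. Protocol 3.5 bases the RP2D on all the clinical evidence. That the unconfirmed ORR enters the posterior is itself an inference, drawn because it is the only RECIST ORR defined.

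**The size depends on assumptions.** It is tempting to say that unconfirmed responses double the apparent probability of success. That holds only if one third of responses fail, at the 25% threshold, in 18 patients. At 20% or 15%, or with pooled cohorts, the change is smaller.

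**Error is not all one way.** SAP 8.1.3 notes that early inflammation can make tumors look larger in patients who later respond, so RECIST may also understate activity. Confirmation brings a downward error of its own by losing genuine last-scan responses. This is a good reason to keep the unconfirmed row.

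**Persistence is partly visible already.** Patient listings and descriptive duration of response are planned. They help with 18 patients, but they do not give a confirmed rate.

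What remains is narrower: the cohort's main efficacy endpoint has no confirmed version, and the plan does not say which ORR the posterior uses.

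**Conclusion.** The point holds as a low-cost improvement and is not an error in the plan. The reason for the waiver is true but does not address the use that SAP 4.3 makes of ORR in Cohort 3B. Unconfirmed best response over all scans tends to raise ORR, and nothing planned shows by how much.

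Under the assumed loss of one or two responses from the 6/18 example, the probability of exceeding 25% falls by 17 or 39 percentage points (0.797 to 0.623 or 0.410). For 20% the fall is 11 or 30 points (0.915 to 0.801 or 0.615). For a pooled 11/33 at 25% it is 10 or 24 points (0.865 to 0.764 or 0.630). These figures rest on an illustrative responder count and an assumed number of failures; they do not predict the trial's result.

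A reader might go further and conclude that confirmed ORR should replace the pre-specified one. The documents do not support that. They do not say whether the thresholds come from confirmed or unconfirmed rates, and a confirmed ORR set against unconfirmed thresholds would create a mismatch in the other direction.

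**What to change.** 1. **SAP 8.1.3, item 2:** also derive a confirmed RECIST 1.1 best overall response, requiring a second CR or PR at least 4 weeks after the first, from the scheduled 8-weekly scans. Show a confirmed CR+PR row beside the unconfirmed one.
2. **SAP 4.3:** state which ORR enters the Jeffreys posterior, and compute the posterior for both versions.
3. **SAP 4.3:** for each ORR threshold, state whether it is a confirmed or an unconfirmed rate, and compare it with the ORR on the same basis.
4. **Any pooled analysis of Cohorts 7A and 3B:** apply the same two rows.

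The cost is SAP wording and one extra derivation; no additional imaging is needed. The confirmed row will omit a response first seen at a participant's last scan, and showing both rows keeps such cases visible.
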